11. INDEPENDENT SAFETY COMMITTEES

Clinical Events Committee

An independent (3-Member) Clinical Events Committee (CEC) will be established to oversee the safety progress. Members of the CEC must be free of significant conflicts of interest (e.g. Financial, intellectual, professional, or regulatory), and are experts in all scientific disciplines needed to interpret the data and ensure study participant safety. The CEC will meet via teleconference a minimum of two (2) times over the course of the study. The CEC may also meet for an ad hoc review of data in the event that a UADE is reported. The CEC charter will be maintained by the Sponsor as part of the clinical study project plan. The CEC charter will outline membership and voting procedures as well as CEC Meeting documentation and communication.

The CEC will perform the following activities:

- Adjudicate all adverse events based on whether the events were:
 - Serious/Non-Serious
 - Anticipated/Unanticipated
 - Related to procedure and/or device

•

The CEC will convene to provide an immediate adjudication [within 48 hours] of unanticipated adverse device effects [UADE] in terms of anticipation, severity and relatedness to study devices.

POGO Study		
Study #2019-08		

Data Safety Monitoring Board

An independent (4-Member) Data Safety Monitoring Board (DSMB) will be established to oversee the Study outcome. Members of the DSMB must be free of significant conflicts of interest (e.g. Financial, intellectual, professional, or regulatory) and are experts in all scientific disciplines needed to interpret the data and ensure study participant safety, including an independent biostatistician. The DSMB will meet via teleconference a minimum of one (1) time over the course of the study. The DSMB manual of operation (MOP) will be maintained by the Sponsor as part of the clinical study project plan. The DSMB MOP will outline membership and voting procedures as well as DSMB Meeting documentation and communication. The DSMB meetings will include an open session where the Sponsor will present study updates, review trends for device malfunctions, protocol deviations and subject withdrawal reasons to communicate study progress. The Investigators may attend the open session.

In addition to the open portion of the DSMB meetings, there will be closed sessions that will only be attended by the DSMB members.

The DSMB will perform the following activities during the closed session of the meetings:

- Assess primary safety endpoint
- Assess participant risk versus benefit, performance of study sites, and other factors that can affect study safety outcome
- Review factors external to the study when interpreting the data, such as scientific or therapeutic
 developments that may have an impact on the safety of the participants or the ethics of the study
- Make recommendations to Edwards Lifesciences, IRB, and investigators concerning continuation or conclusion of the study based solely on safety evaluation
- Protect the confidentiality of the study data and the results of monitoring

To mitigate any potential release of study results, the analysis of safety endpoint will be led by the independent biostatistician serving on the DSMB. The biostatistician will have no contact with the Sponsor or any study sites. Furthermore, the identification of the other DSMB members will not be shared with the sites during the conduct of the study.

Stopping Rules

Continuation or discontinuation of the study will be based upon the DSMB's evaluation of study safety. The DSMB may recommend stopping the study based solely on any safety concerns.

THIS DOCUMENT CONTAINS CONFIDENTIAL AND PROPRIETARY INFORMATION OF EDWARDS LIFESCIENCES, LLC. IT MAY NOT BE REPRODUCED OR DISCLOSED WITHOUT PRIOR WRITTEN PERMISSION FROM EDWARDS LIFESCIENCES, LLC.

POGO Study	
Study #2019-08	

12. DATA HANDLING AND RECORD KEEPING

Confidentiality

Information about Study subjects will be kept confidential and managed according to the requirements of the Health Insurance Portability and Accountability Act of 1996 (HIPAA). Consistent with these regulations, a signed authorization will be obtained that informs each subject of the following:

- What protected health information (PHI) will be collected from subjects in this Study
- Who will have access to that information and why
- Who will use or disclose that information
- The rights of a research subject to revoke their authorization for use of their PHI

No subject demographic data or medical information will be used or shared outside the Sponsor and site staff unless an unanticipated adverse device effect (UADE) is reported. If a UADE is reported, all efforts will be made to keep subject information confidential. The Sponsor is dedicated to maintaining the confidentiality and privacy of subjects who volunteer to participate in the Study. The Study Investigator and the Study site personnel are responsible for maintaining confidentiality throughout the clinical Study. The Sponsor and Sponsor designated Study personnel will have access to the data collected. The hard copies of the source documentation are to be maintained in a secure area with limited access.

To protect subject confidentiality, the subject's name must not appear anywhere on CRFs, or supporting documentation removed from the site. All subject identifiers (e.g., social security number) will be obliterated from all photocopies of source documents that have been removed from the site. All Study documents will identify the subject by a subject Study identification number and Protocol number assigned by the Sponsor (if applicable).

In the event that a subject revokes authorization to collect or use PHI, the Investigator, by regulation, retains the ability to use all information collected prior to the revocation of subject authorization. For subjects that have revoked authorization to collect or use PHI, attempts should be made to obtain permission to collect at least vital status (i.e. that the subject is alive) at the end of their scheduled Study period.

POGO Study		
Study #2019-08		

Source Documents

Source data are all information, original records of clinical findings, observations, or other activities in a study necessary for the reconstruction and evaluation of the study. Source data are contained in source documents. Examples of these original documents, and data records include: hospital records, clinical and office charts, laboratory notes, memoranda, subjects' diaries or evaluation checklists, pharmacy dispensing records, recorded data from automated instruments, copies or transcriptions certified after verification as being accurate and complete, microfiches, photographic negatives, microfilm or magnetic media, x-rays, subject files, source worksheets that have been certified as source, and records kept at the pharmacy, at the laboratories, and at medical-technical departments involved in the study.

Required data for this Study are to be recorded in the subject's file and/or in worksheets, certified as source, for source documentation and data verification unless otherwise specified. Protocol deviation information can be recorded directly on the Protocol Deviation eCRF. Some of the source documentation generated during the Study may be either a worksheet, the electronic data from the Monitor, laboratory data, or printout from Radiometer and YSI. It is recommended that electronic case report forms (eCRFs) be completed within 24 hours of data availability, but not more than 10 working days after completion of assessments. Because of the potential for errors, inaccuracies, and illegibility in transcribing data onto eCRFs, the Investigator must permit inspection of the source documents.

POGO Study	
Study #2019-08	

13. DATA COLLECTION METHODS

Study data will be captured utilizing electronic Case Report Forms (eCRFs) including the 30-day follow-up call as well as downloaded files captured directly via the use of the HemoSphere advanced monitor. Data collected from the HemoSphere advanced monitor will be downloaded at the end of each catheterization procedure and stored on a USB stick. USBs will be stored in a secure location at the site, accessible only to Study site personnel. The HemoSphere data on USBs may be shipped to the Sponsor at any point in time of the study per the request of the Sponsor.

POGO Study	
Study #2019-08	

14. RECORD RETENTION

It is the Investigator's responsibility to retain Study essential documents during the investigation and for a minimum period of two (2) years after the investigation is terminated or completed, or the records are no longer required for the purposes of supporting a premarket approval application or a notice of completion of a product development protocol. These documents should be retained for a longer period if required by an agreement with the Sponsor. In such an instance, it is the responsibility of the Sponsor to inform the Investigator/institution as to when these documents no longer need to be retained.

POGO Study	
Study #2019-08	

15. STUDY DOCUMENTATION

Study Records

Edwards will maintain accurate, complete, and current records relating to the conduct of the study. Records to be maintained by Edwards Lifesciences and the study site include but are not limited to:

- Study protocol and all amendments, if applicable
- IRB approved Informed Consent
- IRB approval letter, including informed consent form
- IRB membership list, or alternative notification of IRB being duly constituted or Department of Health and Human Services Multiple Projects Assurance Number
- IRB correspondences
- Study training logs
- Device accountability records
- Required reports, if applicable

The following records must be maintained for each subject enrolled in the study:

- Signed informed consent form
- All completed eCRFs
- Supporting documentation of any adverse events

Study Reports

Designated site personnel shall prepare and submit the following accurate and complete reports in a timely manner to the IRB and FDA, if applicable:

- Report of an Unanticipated Adverse Device Effects (UADEs) as soon as possible, but in no event later than 10 working days after the first awareness of the event. After an internal evaluation, Edwards shall report the results of such evaluation to FDA and to all reviewing IRBs and participating investigators within 10 working days after receipt of notice of the effect.
- Withdrawal of IRB approval within 5 working days to Edwards. Thereafter, Edwards shall notify FDA
 and all reviewing IRBs and participating investigators of any withdrawal of approval of an investigation
 or a part of an investigation by a reviewing IRB within 5 working days after receipt of the notification
 of withdrawal of approval.
- Progress reports will be submitted to the IRB as required and no less than yearly.
- Deviation from the study protocol to protect the subject's life or physical well-being in an emergency will be reported to Edwards as soon as possible, but in no event later than 5 working days after the emergency occurred. Non-emergency deviations will be reported to the IRB, as required. If deviations may affect the scientific soundness of the plan or the rights, safety, or welfare of human subjects, FDA and IRB shall be notified.
- A final written report is submitted to the IRB within 6 months after completion or termination of the study as required.
- Upon request by the reviewing IRB or FDA, Edwards will provide accurate, complete, and current information about any aspect of the investigation.

THIS DOCUMENT CONTAINS CONFIDENTIAL AND PROPRIETARY INFORMATION OF EDWARDS LIFESCIENCES, LLC. IT MAY NOT BE REPRODUCED OR DISCLOSED WITHOUT PRIOR WRITTEN PERMISSION FROM EDWARDS LIFESCIENCES, LLC.

 POGO Study]
Study #2019-08	

 Use of the study device without informed consent will be reported to Edwards and the IRB within 5 working days after the use occurs. Thereafter, Edwards shall notify FDA within 5 days of receipt of notice.

THIS DOCUMENT CONTAINS CONFIDENTIAL AND PROPRIETARY INFORMATION OF EDWARDS LIFESCIENCES, LLC. IT MAY NOT BE REPRODUCED OR DISCLOSED WITHOUT PRIOR WRITTEN PERMISSION FROM EDWARDS LIFESCIENCES, LLC.

POGO Study	
Study #2019-08	

Communication Procedures

Edwards will utilize an electronic regulatory binder to maintain required study documentation including applicable correspondences during the course of the study.

POGO Study	7
Study #2019-08	

16. STUDY MONITORING, AUDITING AND INSPECTING

Site Selection

The Study site(s) for this Study will be pre-screened by the Sponsor. The Principal Investigator will be selected based on their training and experience with this type of research activity and available subject population. The Sponsor will provide the Investigator with information, Study specific training, and supplies necessary to conduct the Study.

Study Monitoring Plan

A Monitoring Plan will be created to address monitoring arrangements and the extent of source data verification. A Study monitor will be assigned to monitor the progress of the Study by the Sponsor. The Study monitor may be either an employee of the Sponsor or contracted. The Study monitor will be responsible for reviewing eCRFs and monitoring the Study site routinely to observe Study progress and compliance with Study Protocol. The Investigator must permit inspection of the source documents, regulatory binders and other Study related documents provided by the Sponsor.

Study monitoring visits will be scheduled throughout the duration of the Study between the Study monitor and the Investigator and/or Designee at a mutually convenient and available time. These visits will assure that the facilities are still acceptable, the Protocol and investigational plan are being followed, the IRB has been notified of approved Protocol changes as required, complete records are being maintained, appropriate timely reports have been made to the Sponsor and the IRB, device and device inventory are secure and the Investigator is carrying out all agreed activities. Any personnel changes must be reported to the Study monitor immediately.

All eCRFs will be maintained in a validated EDC system and missing or unclear data will be queried as necessary throughout the Study. The Sponsor may request further information and documentation when complications and/or malfunctions are observed and reported.

Interim Monitoring Activities

The Sponsor has the obligation to monitor the conduct of this study to ensure that the study is conducted in accordance with the protocol, Edwards Lifesciences procedures and 21 CFR 812.46 Monitoring Investigations.

Interim monitoring visits (onsite or remote) will be conducted to evaluate the progress of the study, verify the rights, well-being, and protection of the patients, and verify that the reported clinical study data is accurate, complete and verifiable from the electronic medical records and source documents. Monitoring visits will be made in accordance with the Monitoring Plan.

Site Close-Out Visit

The Investigator will be notified in writing upon termination or completion of the Study. The Sponsor retains the right to suspend or prematurely terminate this clinical investigation at any time. Upon completion or premature termination of the Study, the Study monitor will perform a close-out visit.

THIS DOCUMENT CONTAINS CONFIDENTIAL AND PROPRIETARY INFORMATION OF EDWARDS LIFESCIENCES, LLC. IT MAY NOT BE REPRODUCED OR DISCLOSED WITHOUT PRIOR WRITTEN PERMISSION FROM EDWARDS LIFESCIENCES, LLC.

POGO Study	
Study #2019-08	

A site will be considered closed when the following criteria are met:

- Last subject completes 30-day follow-up
- All data queries are resolved
- A site closeout visit is completed
- The IRB is notified in writing of site and study closure in accordance with their requirements

Auditing and Inspecting

In the event that audits are initiated by the Sponsor or national/international regulatory authorities, the Investigator shall allow access to the original medical records and provide all requested information, as applicable. The Investigator will permit Study-related monitoring, audits, and inspections by the Research Quality Assurance Office, IRB, the Sponsor, and government regulatory bodies, of all Study related documents (e.g. source documents, regulatory documents, data collection instruments, Study data etc.). The Investigator will ensure the capability for inspections of applicable Study-related facilities (e.g. pharmacy, diagnostic laboratory, etc.).

POGO Study	
Study #2019-08	

17. ETHICS

Ethical and Scientific Conduct of the Clinical Research Study

The Study may only commence once IRB approval and regulatory approval, as applicable, are received. This Study will be conducted in compliance with the Protocol approved by the IRB, the relevant federal regulations, and IRB policies and procedures and according to Good Clinical Practice standards.

The Investigator shall ensure that all work and services described herein, or incidental to those described herein, shall be conducted in accordance with the highest standards of medical and clinical research practice and the applicable regulations. The Investigator will provide copies of the current Study Protocol to all Study site personnel responsible for Study conduct.

As the Sponsor of this clinical Study, Edwards Lifesciences has the overall responsibility for the conduct of the Study, including assurance that the Study meets the regulatory requirements of the pertinent regulatory agencies. Edwards Lifesciences will also ensure compliance with the signed clinical agreement, the Protocol, the requirements of applicable regulations, and any conditions of Study approval by the IRB.

The Sponsor may transfer study related duties and functions to a CRO. Transferred duties and functions will be specified in a written agreement. Ultimate responsibility for the quality and integrity of the Study resides with the Sponsor.

POGO Study	
Study #2019-08	

18. FINANCIAL DISCLOSURES

Appropriate financial disclosures will be obtained from all Principal Investigators and Sub-Investigators and additional personnel listed on the Statement of the Investigator. The Investigator will provide sufficient and accurate financial disclosure information to the Sponsor.

POGO Study		
Study #2019-08		

19. PUBLICATIONS

At the conclusion of the Study, a manuscript may be prepared for publication in a scientific journal. The Sponsor reserves the right to review any manuscripts prior to submission. The Study will be entered into a clinical trial registry databank such as clinicaltrials.gov.

POGO Study	
Study #2019-08	

20. ACRONYMS AND ABBREVIATIONS

Acronym	Entire Word
ADE	Adverse Device Effect
AE	Adverse Event
ASA	American Society of Anesthesiologists
BP	Blood Pressure
CI	Cardiac Index
CCO	Continuous Cardiac Output
CO	Cardiac Output
CEC	Clinical Events Committee
CRF	Case Report Form
DSMB	Data Safety Monitoring Board
FDA	Food and Drug Administration
eCRF	Electronic Case Report Form
EDC	Electronic Data Capture
GCP or gCP	Good Clinical Practice
HIPAA	Health Insurance Portability and Accountability Act
HR	Heart Rate
Hr	Hour
ICC	Intra-Cluster Correlation
ICF	Informed Consent Form
ICO	Intermittent Cardiac Output
ICU	Intensive Care Unit
IRB	Institutional Review Board
ITT	Intent-to-Treat
mL	Milliliters
mITT	Modified Intent-to-Treat
N	Total Sample Size
NCT	National Clinical Trial
PAC	Pulmonary Artery Catheters
PI	Principal Investigator
PR	Pulse Rate
SADE	Serious Adverse Device Effect
SAE	Serious Adverse Event
SAP	Statistical Analysis Plan
SpO2	Peripheral Capillary Oxygen Saturation
Sub-I	Sub-Investigator
SV	Stroke Volume
SVI	Stroke Volume Index
SVV	Stroke Volume Variation
SVR	Systemic Vascular Resistance
UADE	Unanticipated Adverse Device Effect

THIS DOCUMENT CONTAINS CONFIDENTIAL AND PROPRIETARY INFORMATION OF EDWARDS LIFESCIENCES, LLC. IT MAY NOT BE REPRODUCED OR DISCLOSED WITHOUT PRIOR WRITTEN PERMISSION FROM EDWARDS LIFESCIENCES, LLC.

POGO Study	
Study #2019-08	

		Exploratory Analyses	2	
		Interim analysis	2	
•	8.6	Analysis of other hemodynamic parameters	2	
9.		S OF SAFETY	2	
	9.1	Deaths	2	
44	9.2	Adverse Events	Error! Bookmark not defined	
	REFEREN		2	
	APPENDI		2	
		JRE SEARCH/REVIEW	2	
14.	YEEK KE	VIEW REQUEST, PER SAP INSTRUCTION (DOC	-0089205) 2	Õ

Revision Date: December 2, 2020

Rev B

For Use Only by Affiliates of Edwards Lifesciences

Page 4

Title

Statistical Analysis Plan for A Prospective, Single-Arm, Nonrandomized, Observational Study of Cardiac Output Monitoring in Pediatric Patients

Glossary of Terms

ABBREVIATION	DEFINITION OR DESCRIPTION
ABP	Arterial Blood Pressure
AE	Adverse Event
ADE	Adverse Device Effect
Alpha	Type I error in hypothesis test
Beta	Type II error in hypothesis test
BSA	Body Surface Area
CEC	Clinical Events Committee
CI	Cardiac Index
CI	Confidence Intervals
CO	Cardiac Output
CSR	Clinical study report
eCRF	Electronic Case Report Form
GCP	Good Clinical Practice
H0	Null hypothesis
H1	Alternative hypothesis
MAP	Mean Arterial Pressure
ICC	Intra-cluster correlation coefficient
IRB	Institutional Review Board
PAC	Pulmonary Artery Catheter
PE	Percent Error
SAE	Serious Adverse Event
SAP	Statistical Analysis Plan
SD	Standard Deviation
SV	Stroke Volume
TD	Thermodilution

	Revision Date: De	ecember 2, 2020	Rev	В	For Use Only by Affiliates of Edwards Lifesciences	Page 5
Edwards	Title	Statistical Analysis P Nonrandomized, Obso Monitoring in Pediatri	ervatio	onal St		

1. INTRODUCTION

This statistical analysis plan (SAP) specifies the statistical methods to be implemented for the analysis of data collected within the scope of Edwards Lifesciences's Protocol #2019-08, "A Prospective, Single-Arm, Nonrandomized, Observational Study of Cardiac Output Monitoring in Pediatric Patients", and provides detailed instructions as to how each analysis will be performed.

Results obtained from the analyses specified in the SAP will become the basis of the clinical study report (CSR) for this protocol. Any deviations from the SAP must be documented in the CSR.

2. STUDY DESIGN

2.1 Study Objectives

[figure not shown]
The primary objective of the study is to assess Cardiac Output Monitoring in pediatric subjects by comparing FloTrac[™] and ClearSight[™] to intermittent thermodilution Swan-Ganz[™], in order to expand the indications of FloTrac[™], ClearSight[™] and Swan-Ganz Intermittent Thermodilution Catheter to the pediatric population 12 to 18 years of age.

2.2 Overall Study Design and Plan

This is an observational study in the U.S. A subject will be considered enrolled in the study once the subject has signed the informed consent, a Swan-Ganz catheter has been deployed, a FloTrac has been connected, a ClearSight finger cuff has been attached and ForeSight Elite sensors have been placed. The Study ID will be a 6-digit number, the first three numbers will identify the site, and the second set of numbers will identify the subject identification number. Subjects will be enrolled in age group, 12 to 18 years of age.

A Swan-Ganz catheter, FloTrac transducer, ClearSight finger cuff and ForeSight Elite sensors will be placed prior to the start of the surgery. There will be 2 sets of 4 intermittent cardiac output measurements recorded, each over a 30 second interval during the bolus injection. Measures for FloTrac and ClearSight will be retrospectively matched by time point to the Swan-Ganz catherization data. Intermittent cardiac output and other hemodynamic parameters will be collected throughout the duration of the surgery. For each study subject two sets of four repeated measurements will be taken in the cardiac catherization lab. Data collected in this study will support in expanding the current indications of Swan-Ganz, FloTrac and ClearSight into the pediatric population.

In order to avoid a learning curve bias, up to 6 roll-in subjects will be enrolled, which is counted in the final sample size in study. The collected data from the roll-in cohort will be analyzed separately from the pivotal study subjects.

A modified intent-to-treat (mITT) principle will be applied. Through investigator professional judgement and statistical principles, this study will be conducted in a manner that is consistent with the applicable regulations and in accordance with current Good Clinical Practice (GCP).

All methods of measurements will be recorded for all devices and included as part of the data set. Edwards will conduct analyses both with and without observations that are determined to be outliers. Once outliers are identified, the Principal Investigator will assess the validity of the data.

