3. STUDY ENDPOINTS

The primary effectiveness endpoint is to demonstrate that monitoring of cardiac output (CO) with Swan-Ganz, FloTrac, and ClearSight is comparable as determined by the Bland-Altman method of bias.

The secondary endpoint analyses will include:

CO, assessed using include using the Critchley and Critchley method of percent error calculation

Two comparisons will be performed for each of three endpoints described above: FloTrac vs Swan-Ganz and ClearSight vs Swan-Ganz.

The primary and secondary efficacy endpoints will be analyzed using the evaluable analysis set as defined in Section 5.

The primary safety endpoint is to assess all serious intraoperative and post-operative adverse events through 30 days, including serious device-related events. The safety endpoint will be analyzed using the safety analysis set as defined in Section 5.

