5.2. Evaluable Subject

An evaluable subject is one who has valid CO pair measurements that were not rejected and also has completed the 30-Day follow up.

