6.3 Handling of Invalid Data

After downloading the data from the hemodynamic monitors, abnormal observations will be checked and evaluated for hemodynamic stability. Should there be any instability, the result will be rejected. All data will be recorded, and any rejected values will be clearly identified in the eCRF.

The rejection criteria that will be used to determine - hemodynamic instability are detailed below:

- Mean arterial pressure (MAP): If MAP varies > 15% during the 30-sec period of each intermittent thermodilution, the bolus will be rejected.
- Pulse rate: If Pulse varies > 15% during the 30-sec period of each ITD, the bolus will be rejected.
- PhysioCal: If PhysioCal is not at least 30 beats, the bolus will be rejected.

•

Upon taking four (4) thermodilution measurements and given the above criteria for classifying data as invalid, Edwards proposes to remove the one measurement that is the greatest outlier of the four. If upon the rare occasion two or more outliers measure greater than 15% from the mean, within a series of measurements, or hemodynamic instability results when these observations are taken, the clinician will repeat the series. If this scenario of repeating the series is missed by the clinican during the clinical procedure and discovered by the statisticians during data review, the outliers will be analyzed separately. In addition to the results for the collected parameters, the number of subjects with less than 3 and number of subjects with at least 3 valid values, and results of subjects will be tabulated separately, and reported. Those subjects who have less than 3 valid measurements and were missed for repeated testing by the clinician performing the thermodilutions will be considered as protocol deviations or protocol violations.

Additionally, a supplementary exploratory analysis will be reported using all the recorded values (valid and invalid) to assess the impact of the excluded values.

[figure not shown]

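### The investigator's validity judgement on outliers has no definition, criteria or stated masking, and it can enter the analysis that decides the primary endpoint

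*Combined protocol and SAP*

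**What the plan says.** SAP 2.2 says that "Edwards will conduct analyses both with and without observations that are determined to be outliers", and continues: "Once outliers are identified, the Principal Investigator will assess the validity of the data". That section does not define an outlier or rank the two analyses.

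Other sections bear on the same question:

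- **Analysis set.** SAP 3: "The primary and secondary efficacy endpoints will be analyzed using the evaluable analysis set as defined in Section 5". SAP 5.2: "An evaluable subject is one who has valid CO pair measurements that were not rejected and also has completed the 30-Day follow up". SAP 4 and the Analysis Populations text in protocol section 6 describe the set in similar terms.
- **Numeric rejection rules.** SAP 2.2.1 and 6.3 reject a bolus if mean arterial pressure or pulse varies by more than 15% in the 30-second window, or if Physiocal is below 30 beats. They also use a 15% distance from the series mean. Within a series, "Edwards proposes to remove the one measurement that is the greatest outlier of the four".
- **All recorded values.** SAP 6.3: "a supplementary exploratory analysis will be reported using all the recorded values (valid and invalid) to assess the impact of the excluded values".
- **A competing population.** SAP 2.2 invokes a modified intent-to-treat principle, and SAP 5.3 places every exposed subject in the effectiveness dataset.
- **The primary test.** SAP 8.1.2 gives the hypotheses and the one-sample t-test but names no dataset.

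**The concern.** The result of an agreement study is the distribution of the between-device differences, and the extreme differences carry much of the information. The plan already has numeric rules for discarding a measurement. SAP 2.2 adds a second, undefined step: someone identifies outliers, and the investigator then decides whether the data are valid. SAP 5.2 makes validity a condition of being evaluable, so this decision can determine which differences enter the primary test.

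If the decision is made with the paired device value in view, even unintentionally, exclusions can favour agreement. Mean bias could move towards zero, the limits of agreement would narrow, and percent error, which SAP 3.2.1 builds from absolute differences, would fall. The analysis that would escape this effect is the one labelled exploratory.

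**Working it through.** **Step 1. Trace which analysis decides.**

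1. SAP 3 puts the primary endpoint on the evaluable set.
2. SAP 4 and 5.2 limit that set to valid pairs that were not rejected.
3. SAP 6.3 makes the analysis of all recorded values, valid and invalid, supplementary.
4. The valid-pair analysis is therefore the primary one on the most natural reading.
5. SAP 6.3 ties invalidity to the numeric criteria. SAP 2.2 separately gives the investigator a validity assessment of outliers. No text says whether these are the same values, or whether the investigator may add to or override the numeric rules.
6. SAP 5.3, read literally, puts all exposed subjects in the effectiveness dataset, which does not fit items 1 and 2.

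**Step 2. Reproduce the design figure.** SAP 2.3.1 needs 60 subjects and allows for 34.5% rejection and 10% loss:

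60 / [(1 − 0.345) × (1 − 0.10)] = 60 / 0.5895 = 101.8, rounded up to 102. This matches the plan, so n = 60 is a fair basis for the illustration.

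**Step 3. Find how large an observed bias still passes.** Inputs from SAP 2.3.1 are a margin of 0.5 L/min and an SD of 0.991 after the repeated-measures adjustment. The standard error is 0.991 / √60 = 0.128.

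- At 0.025 per side: 0.5 − 2.001 × 0.128 = about 0.24 L/min.
- At 0.0125 per side (the two-sided 97.5% interval of SAP 3.1.2): 0.5 − 2.300 × 0.128 = about 0.21 L/min.

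**Step 4. Illustrate the effect of exclusions.** The plan gives no outlier rule, so the number and pattern removed are assumptions: 3 of 60 subject-level differences (5%), drawn from a normal distribution with SD 1.0, in 40,000 simulated samples.

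| Removal | Shift in mean | SD after removal | Change in SD |
|---|---|---|---|
| Three highest | −0.104 | 0.90 | −10% |
| Three largest in absolute size, true bias 0 | about 0 | 0.87 | −13% |

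The one-sided shift is 0.104 / 0.5 = about a fifth of the margin. On the SD scale, with the 1.984 multiplier of SAP 8.1.3, the half-width of the limits of agreement falls from 1.984 × 1.0 = 1.98 to 1.984 × 0.87 = 1.73 L/min in the second case.

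**Step 5. Translate to the test (0.025 per side).**

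- True bias at the 0.5 margin: removing the three highest raises false success from 0.025 to about 0.15.
- True bias 0.3: the same removal raises the pass rate from about 33% to 69%.
- True bias at the margin, removing the three differences furthest from the true mean in either direction: false success stays at about 0.025.
- True bias 0: removing the three highest moves the mean away from zero, so it does not help the device.

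With a 2 to 3 SD cut applied to both tails, true bias 0.3, and normal or heavier (t with 5 degrees of freedom) tails, the with- and without-outlier analyses disagree in about 2% to 21% of simulated trials. The range reflects the cut-off and tail assumptions.

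**The case against.** The strongest case on the other side has four parts.

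**The deciding analysis is not left open.** A reader might infer from SAP 2.2 alone that the plan never says whether the analysis with or without outliers decides. The documents do not support that. SAP 3, 4, 5.2 and 6.3 together make valid, non-rejected pairs primary and the all-values analysis supplementary. This part stands. What remains open is whether the investigator's judgement is part of being valid.

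**Nobody is said to see the paired values.** A reader might infer that the investigator is unmasked to the differences. No section says so. SAP 2.2.1 names arterial pressure, pulse rate and Physiocal as displayed, and SAP 2.2 matches the test-device values retrospectively. The supportable statement is that no masking is described.

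**Late-found outliers are a different matter.** SAP 6.3 says of values "discovered by the statisticians during data review, the outliers will be analyzed separately". These are thermodilution values far from the mean of their own series, or taken during instability, where the repeat was missed. They are not large between-device differences, and that sentence should not be used as evidence of selective removal.

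**Selective exclusion would probably be visible.** SAP 3.1.2 compares bootstrap intervals with and without rejected data, SAP 6.3 reports the impact of excluded values, and SAP 8.3.1 removes one or a few subjects to look for influence. These are real safeguards for disclosure. They carry no decision rule, so they would show a discrepancy without settling which result counts.

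**Conclusion.** The point holds in a limited form. SAP 2.2 gives the investigator an undefined, after-the-fact validity judgement with no stated masking and no link to the numeric rules, and SAP 5.2 allows that judgement to reach the deciding analysis. SAP 5.3 adds a conflicting population.

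The size is illustrative only. The 0.10 L/min shift arises only if all three assumed removals lie on one side; it is not an expected effect and should not be read as one. Removal balanced between the tails leaves the expected mean where it was but still cuts the SD by about 13% in the example, which flatters the limits of agreement. Since a trial of 60 passes only below roughly 0.21 to 0.24 L/min observed bias, a one-sided shift of that order would matter if it occurred. Nothing in the documents shows that it would. This is an inexpensive improvement, not a defect that undermines the design.

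**What to change.** - **SAP 8.1.2:** state that the primary analysis includes every pair that passes the numeric rules of SAP 2.2.1 and 6.3.
- **SAP 2.2:** define an outlier and say how the term relates to the rejected values of 2.2.1 and 6.3. Require any further validity decision to rest on curve and trace quality, without sight of the paired device value, and to be documented before differences are computed.
- **Ranking:** label the analysis that leaves out those further values as a sensitivity analysis.
- **Populations:** reconcile the modified intent-to-treat wording in SAP 2.2 and 5.3 with the evaluable set in SAP 3, 4 and 5.2.

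The cost is SAP wording and a masked listing for the validity review. No extra subjects or measurements are needed. The limits of agreement may come out slightly wider than they would with discretionary exclusions.
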